11.8.5. Frequency of interferon-gamma- secreting antigen-reactive cells by ELISPOT

The list of analytes below are for classification of participants and for determining the quality of cells, and hence will be listed only.

Lab Test (LBTEST)	Lab Test Code (LBTESTCD)	Units	Derived	Details
Viable Cells Count	VIABCC	Count		
Viable Cells/Total Cells	VIABCCE	%		

The list of analytes below will listed. PARAM/PARAMCD will be created from LBTEST/LBTESTCD and the stimulus (e.g. EBV) which is stored in SUPPLB.

Lab Test (LBTEST)	Lab Test Code (LBTESTCD)	Units	Derived	Details
Interferon Gamma Spot Forming Cell Count	IFNGSFCC	count/10 ⁶ PBMC		

The following stimulants have been used:

- Unstimulated
- GAD – Glutamic Acid Decarboxylase
- icIA-2 – Intracellular Islet Antigen-2
- EBV – Epstein Barr Virus
- PI – Pro-insulin
- PI C-pep – Pro-insulin-derived C-peptide
- PPI Leader – Prepro-insulin Leader

11.8.6. Quantification of serum cytokines and soluble cytokine receptors

The list of analytes below will be summarised and analysed as per Section [9.4](#)

Lab Test (LBTEST)	Lab Test Code (LBTESTCD)	Units	Derived	Details
Interferon Gamma (ng/L)	IFNG	(ng/L)		
Soluble Interleukin 6 Receptor (ng/mL)	IL6SR	(ng/mL)		
Interleukin 6 Signal Transducer (ng/mL)	IL6ST	(ng/mL)		Soluble gp130
Interleukin 10 (ng/L)	INTLK10	(ng/L)		
Interleukin 12 (ng/L)	INTLK12	(ng/L)		
Interleukin 13 (ng/L)	INTLK13	(ng/L)		
Interleukin 1 Beta (ng/L)	INTLK1B	(ng/L)		
Interleukin 2 (ng/L)	INTLK2	(ng/L)		
Interleukin 4 (ng/L)	INTLK4	(ng/L)		
Interleukin 6 (ng/L)	INTLK6	(ng/L)		
Interleukin 8 (ng/L)	INTLK8	(ng/L)		

11.8.7. TCR deep sequencing

The list of analytes below will be summarised and analysed as per Section 9.1.1.2.

Test (PFTEST)	Test Code (PFTESTCD)	Units	Derived	Details
Productive Clonality	AH001	%		

Further TCR deep sequencing endpoint may be explored through Adaptive Biotechnology's ImmunoSeq™ Analyser but these are considered as further exploratory work outside of this RAP.

11.8.8. Suppressive activity of regulatory cells

The list of analytes below will be listed only. PARAM/PARAMCD will be created from LBTEST/LBTESTCD and the Stimulus (Treg:Teff) an Stimulus concentrations (e.g. 0:1) which are stored in SUPPLB.

Lab Test (LBTEST)	Lab Test Code (LBTESTCD)	Units	Derived	Details
Count	COUNT	CPM		
Percentage suppression	PCTSUPP	%		

The following stimulus will be used (stored in SUPPLB):

- Treg:Teff

The following stimulus concentrations will be used (stored in SUPPLB):

- 0:1
- 1:1
- 1:2
- 1:4

11.8.9. Number of digits for display of biomarker data

To ensure that the outputs are readable, if the maximum value of the derived variable in the units given in this RAP is < 0.0001 both unit and values may be multiplied with 10^{3n} (n being an integer) so that the maximum value is ≥ 0.0001 .

Otherwise, the following rules will apply:

- All individual continuous and count data will be displayed with three significant digits. Summary statistics will follow the normal IDSL rules, e.g. the mean will be presented with four significant digits.
- The display of percentages variable will depend on the median percentage across all treatments and time points, in the following manner:
 - The number of decimal points will be chosen so that the median as an individual value would be presented with three significant digits (e.g. if the median 20.5% all individual percentages should be displayed with one decimal place).
 - Normal rules for derived summary statistics apply.
 - Any percentage larger than zero which would be displayed as zero according to the above rules will instead be displayed as “<X”, where X is the smallest non-zero percentage that can be displayed.

11.9. Appendix 9: Abbreviations & Trademarks

11.9.1. Abbreviations

Abbreviation	Description
ADaM	Analysis Data Model
AE	Adverse Event
AIC	Akaike's Information Criteria
CDISC	Clinical Data Interchange Standards Consortium
CI	Confidence Interval
CPMS	Clinical Pharmacology Modelling & Simulation
CRS	Cytokine Release Syndrome
CS	Clinical Statistics
CSR	Clinical Study Report
DOB	Date of Birth
DP	Decimal Places
eCRF	Electronic Case Record Form
ECG	Electrocardiogram
EBV	Epstein-Barr virus
IA	Interim Analysis
ICH	International Conference on Harmonisation
IDSL	Integrated Data Standards Library
IMMS	International Modules Management System
INS	Insulin
IP	Investigational Product
ITT	Intent-To-Treat
MMTT	Mixed Meal Tolerance Test
MMRM	Mixed Model Repeated Measures
PBMC	Peripheral Blood Mononuclear Cells
PCI	Potential Clinical Importance
PD	Pharmacodynamic
PDMP	Protocol Deviation Management Plan
PK	Pharmacokinetic
PP	Per Protocol
QC	Quality Control
QTcF	Frederica's QT Interval Corrected for Heart Rate
QTcB	Bazett's QT Interval Corrected for Heart Rate
RAP	Reporting & Analysis Plan
RAMOS	Randomization & Medication Ordering System
SAC	Statistical Analysis Complete
SD	Standard Deviation
SDTM	Study Data Tabulation Model
SOP	Standard Operation Procedure
TA	Therapeutic Area
TFL	Tables, Figures & Listings
ULQ	Upper Limit of quantification

Abbreviation	Description
ULN	Upper Limit of Normal

11.9.2. Trademarks

Trademarks of the GlaxoSmithKline Group of Companies

Trademarks not owned by the GlaxoSmithKline Group of Companies
SAS
SAS/STAT
WinNonlin
Spotfire

11.10. Appendix 10: List of Data Displays

11.10.1. Data Display Numbering

The following numbering will be applied for RAP generated displays:

Section	Tables	Figures
Study Population	1.01 to 1.XX	N/A
Safety	2.01 to 2.XX	2.01 to 2.XX
Efficacy	3.01 to 3.XX	3.01 to 3.XX
Pharmacodynamic	4.01 to 4.XX	4.01 to 4.XX
Biomarker	5.01 to 5.XX	5.01 to 5.XX
Pharmacokinetic	6.01 to 6.XX	6.01 to 6.XX
Section	Listings	
ICH Listings	1 to XX	
Other Listings	XX+1 to ZZ	

11.10.2. Mock Example Shell Referencing

Non IDSL specifications will be referenced as indicated and if required an example mock-up displays provided in [Appendix 11](#): Example Mock Shells for Data Displays.

Section	Figure	Table	Listing
Safety	SAFE_Fn	SAFE_Tn	SAFE_Ln
Efficacy	EFF_Fn	EFF_Tn	EFF_Ln
Pharmacodynamic	PD_Fn	PD_Tn	PD_Ln
Biomarker	BIO_Fn	BIO_Tn	BIO_Ln
Listings			OTHER_Ln

NOTES:

- Non-Standard displays are indicated in the 'IDSL / TST ID / Example Shell' or 'Programming Notes' column as '[Non-Standard] + Reference.'

11.10.3. Deliverable [Priority]

The details provide abbreviations for the 'Delivery Priority' for the various reporting efforts for which displays will be generated.

Abbreviation	Reporting Effort
FA (SAC)	Final Analysis Statistical Analysis Complete

11.10.4. Study Population Tables

Study Population Tables					
No.	Population	IDSL / TST ID / Example Shell	Title	Programming Notes	Deliverable [Priority]
Subject Disposition					
1.01.	Enrolled	ES1	Summary of Subject Disposition for the Subject Conclusion Record	Programmer to update primary reason for withdrawal to be study specific.	FA (SAC)
1.02.	Screened	ES6	Summary of Screening Status and Reasons for Screen Failure		FA (SAC)
1.03.	Enrolled	NS1	Summary of Number of Subjects Enrolled by Country and Site ID		FA (SAC)
1.04.	Enrolled	SP1	Summary of Study Populations		FA (SAC)
1.05.	Safety	DV1	Summary of Important Protocol Deviations	Generated, if data permits. As required, refer to PDMP.	FA (SAC)
1.06.	Safety	SP3	Summary of Exclusions from Per Protocol Population		FA (SAC)
1.07.	Safety	IE1	Summary of Inclusion / Exclusion Criteria Deviations		FA (SAC)
Demographics					
1.08.	Safety	DM1, DM5, DM 11	Summary of Demographic Characteristics, Race and Racial Combinations and Age Ranges	Please combine shells in order DM1, DM5, DM 11. In addition those items please also add the categories for number of positive antibodies at screening (see Section 11.5.3)	FA (SAC)
Medical Conditions					

Study Population Tables					
No.	Population	IDSL / TST ID / Example Shell	Title	Programming Notes	Deliverable [Priority]
1.09.	Safety	MH4	Summary of Past and Current Medical Conditions	We only have current conditions, so need to display only those	FA (SAC)
Concomitant Medications					
1.10.	Safety	CM7	Summary of Concomitant Medications	Split as described in Section 11.3	FA (SAC)
Exposure					
1.11.	Safety	EX1	Summary of Exposure to Study Drug	Also include daily infusion duration in hours for each dosing day	FA (SAC)

11.10.5. Safety Tables

Safety: Tables					
No.	Population	IDSL / TST ID / Example Shell	Title	Programming Notes	Deliverable [Priority]
AE					
2.01.	Safety	AE13	Adverse Event Overview	Split as described in Section 11.3	FA (SAC)
2.02.	Safety	AE15	Summary of All Adverse Events by System Organ Class and Preferred Term	Split as described in Section 11.3 Add a "Any Event" category for each SOC even if not in shell	FA (SAC)
2.03.	Safety	AE15	Summary of Drug-Related Adverse Events	Split as described in Section 11.3 Add a "Any Event" category for each SOC even if not in shell	FA (SAC)
2.04.	Safety	AE16	Summary of Serious Adverse Events by System Organ Class and Preferred Term	Split as described in Section 11.3	FA (SAC)
2.05.	Safety	AE1	Summary of AEs Leading to Permanent Discontinuation of Study Drug or Withdrawal from Study	Do not split this output by phase	FA (SAC)
2.06.	Safety	AE5	Summary of All Adverse Events by Maximum Grade by System Organ Class and Preferred Term	Split as described in Section 11.3	FA (SAC)
2.07.	Safety	AE5	Summary of Drug-Related Adverse Events by Maximum Grade by System Organ Class and Preferred Term	Split as described in Section 11.3	FA (SAC)
Cytokine Release Syndrome					

2.08.	Safety	AE15	Summary of Adverse Events - Cytokine Release Syndrome Induced Symptoms	
 • Definition of Cytokine Release Syndrome in Section 11.5.3 • Overall only, not split by study phase. 	FA (SAC)
Epstein-Barr Virus					
2.09.	Safety	AE15	Summary of Adverse Events Considered to be Potentially Associated with EBV Reactivation	
 • Clinical Symptoms of Mononucleosis AE Terms to include are in Section 11.5.3 • Overall only not split by study phase. 	FA (SAC)
2.10.	Safety	Non-Standard SAFE_T3	Summary of categorical values of Epstein-Barr Virus (Serology: IgG & IgM)	
 • Categories (negative, positive) to be derived from absolute values according to a worst case approach as described in Section 11.5.3 	FA (SAC)
2.11.	Safety	Non-Standard SAFE_T2	Summary of Epstein-Barr Viral Load (PCR)	
 • Geometric Means 	FA (SAC)
2.12.	Safety	Non-Standard SAFE_T4	Categorical Summary of Epstein-Barr Viral Load (PCR)		FA (SAC)

Labs

2.13.	Safety	LB1	Summary of Laboratory Values	
 Order parameters alphabetically. BY Labtype (1. Chemistry, 2. Haematology) 	FA (SAC)
2.14.	Safety	LB1	Summary of Laboratory Changes from Baseline	
 Order parameters alphabetically BY Labtype (1. Chemistry, 2. Haematology) 	FA (SAC)
2.15.	Safety	LB15	Summary of Worst Case Laboratory Results Relative to Normal Range Post-Baseline Relative to Baseline	
 Order parameters alphabetically BY Labtype (1. Chemistry, 2. Haematology) 	FA (SAC)
Electrocardiograms					
2.16.	Safety	EG1	Summary of ECG Findings		FA (SAC)
2.17.	Safety	EG2	Summary of Change from Baseline in ECG Values		FA (SAC)
2.18.	Safety	EG10	Summary of Maximum QTc Values Post-Baseline Relative to Baseline by Category		FA (SAC)
2.19.	Safety	EG11	Summary of Maximum Increase in QTc Values Post-Baseline Relative to Baseline by Category		FA (SAC)
Vital Signs					
2.20.	Safety	VS1	Summary of Change from Baseline in Vital Signs		FA (SAC)
2.21.	Safety	VS7	Summary of Worst Case Vital Sign Results Relative to Potential Clinical Importance (PCI) Criteria Post-Baseline Relative to Baseline		FA (SAC)

Immunogenicity					
2.22.	Safety	Non-Standard EFF_T4	Summary of Immunogenicity	
 With positive instead of responder 	FA (SAC)

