5.3. Patient Specific and Dose Escalation Stopping Criteria

5.3.1. Cytokine Release Syndrome Stopping Criteria

Cytokine Release Syndrome (CRS) experienced during the 6 days of dosing will be monitored specifically by the investigator according to the grading system presented in [Table 5](#) and Section 7.1.5. In-stream real time data review will be utilised, so as to limit patient exposure unnecessarily, if stopping criteria are met.

Table 5 CRS AE Grading System

Adverse Event	Grade 1	Grade 2	Grade 3	Grade 4	Grade 5
Headache	Mild pain	Moderate pain; limiting instrumental ADL	Severe pain; limiting self care ADL	-	-
Fever	38.0 - 39.0 degrees C	>39.0 - 40.0 degrees C	>40.0 degrees C for <=24 hrs	>40.0 degrees C for >24 hrs	Death
Vomiting	1 - 2 episodes (separated by 5 minutes) in 24 hrs	3 - 5 episodes (separated by 5 minutes) in 24 hrs	>=6 episodes (separated by 5 minutes) in 24 hrs	Life-threatening consequences; urgent intervention indicated	Death
Diarrhoea	Increase of <4 stools per day over baseline.	Increase of 4 - 6 stools per day over baseline.	Increase of >=7 stools per day over baseline; incontinence; limiting self care ADL	Life-threatening consequences; urgent intervention indicated	Death
Hypotension	Asymptomatic, intervention not indicated	Non-urgent medical intervention indicated	Urgent medical intervention indicated	Life-threatening and urgent intervention indicated	Death
Chills	Mild sensation of cold; shivering; chattering of teeth	Moderate tremor of the entire body; narcotics indicated	Severe or prolonged, not responsive to narcotics	-	-
Nausea	Loss of appetite without alteration in eating habits	Oral intake decreased without significant weight loss, dehydration or malnutrition	Inadequate oral caloric or fluid intake.	-	-

Adverse Event	Grade 1	Grade 2	Grade 3	Grade 4	Grade 5
Arthralgia	Mild pain	Moderate pain; limiting instrumental ADL	Severe pain; limiting self care ADL	-	-
Myalgia	Mild pain	Moderate pain; limiting instrumental ADL	Severe pain; limiting self care ADL	-	-

ADL= Activities of daily living

Pre-specified CRS individual patient and study dosing stopping criteria are presented in [Table 6](#) and should be followed by the Investigator.

- If individual patient criteria are met: Treatment for that patient will be stopped immediately, will not be restarted, and the patient will be followed up as per protocol.

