7. SAFETY ANALYSES

The safety analyses will be based on the “Safety” population, unless otherwise specified. Due to the long duration of the study safety summaries will be presented for the following time spans: Overall, Dosing Period (defined as day of first dose up to and including day of last received dose of study drug), Post dose up to Week 6, Post-Week 6. A definition is found in Section [11.3](#).

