11.3. Appendix 3: Study Phases

11.3.1. Study Phases

Assessments and events will be classified according to the time of occurrence relative to dosing.

Study Phase	Definition
Pre-Treatment	Date < Date of First Dose
During Dosing	Date of First Dose <= Date <= Date of Final Dose + 1.
Post-dose to Week 6	Date of Final Dose + 1 < Date <= Date of Week 6 Visit ^[1] or Day 42 whichever is greater
Week 6 to Month 24	Date of Week 6 Visit ^[1] or Day 42 whichever is greater < Date <= Month 24 visit.
Safety Follow-up	Date > Month 24
[1] For participants who were consented Prior to Protocol Amendment 4, Day 42 will be used, as they will not have a Week 6 visit.	

Note: for any rule that is relative to dose, the term date also includes time, if recorded. The end date for a visit as recorded in the SV domain will be used for the determining study phase.

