AE = Drug-related	➤ If relationship is marked 'YES' on eCRF OR value is missing.								
Adverse Events : CRS and Clinical Symptoms of Mononucleosis Definition									

 The current MedDRA version at time of database lock will be used for coding of AE's. AEs considered to be related to CRS during the first 14 days post first dose will be determined by medical expert review conducted by the GSK team. For reporting of clinical symptoms of mononucleosis, the following AE's will be extracted based on Preferred Term. In addition, other terms maybe included at the time of reporting. 									
	
  
 Reporting	Preferred Term	Verbatim Terms	
   
 Clinical	Fatigue	Feeling tired & Low energy	
  
	Reporting	Preferred Term	Verbatim Terms	Clinical	Fatigue	Feeling tired & Low energy		
Reporting	Preferred Term	Verbatim Terms							
Clinical	Fatigue	Feeling tired & Low energy							

Adverse Events		
General		
Symptoms of Mononucleosis	Malaise	Feeling unwell
	Myalgia	Joint and muscle pain & Flu like symptoms
	Oropharyngeal pain	Sore throat, throat pain
	Lymphadenopathy	Swollen glands
	Pyrexia	High temperature, Feeling hot and cold & Shivering

Laboratory Parameters

 • All BLQ values will be imputed with $\frac{1}{2}$ LLOQ. • All ALQ values will be imputed with the ALQ + [smallest positive number with the same number of decimal places as the ALQ is reported with] • Values reported as < x are assumed to have an LLOQ of x. • Values reported as > x are assumed to have an ALQ of x.

EBV				

 EBV Serology: 
 Categories (negative, positive) will be derived from absolute IgG and IgM values according to a worst case approach from absolute virus results 				
	QUEST Classification of INDEX	Quest classification of U/ml	BDR Classification of AE/mL	Unified Classification
IgG	< OR = 0.90 NEGATIVE 0.91 - 1.09 EQUIVOCAL > OR = 1.10 POSITIVE		negative : <20 positive : 20 or more	NEGATIVE POSITIVE POSITIVE
IgM	< OR = 0.90 NEGATIVE 0.91 - 1.09 EQUIVOCAL > OR = 1.10 POSITIVE	negative: <36 positive: 36 or more	negative : <20 weakly positive : 20-40 positive : 40 or more	NEGATIVE POSITIVE POSITIVE POSITIVE

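### SAP Table 2.09 counts dosing-period pyrexia and myalgia classed as CRS among potentially EBV-associated symptoms, unmarked and without a phase split: a modest reporting gap that is cheap to close

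*SAP*

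**What the plan says.** SAP 11.5.3 sets two selection rules in the same box.

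- **CRS:** "AEs considered to be related to CRS during the first 14 days post first dose will be determined by medical expert review". This rule has a time window and a clinical judgement.
- **Mononucleosis symptoms:** "the following AE's will be extracted based on Preferred Term". The terms are fatigue, malaise, myalgia, oropharyngeal pain, lymphadenopathy and pyrexia. More terms may be added at reporting. There is no onset window, and nothing is said about events already classed as CRS.

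The CRS events go to Table 2.08 and Listing 21, the mononucleosis terms to Table 2.09 and Listing 22. Tables 2.08 and 2.09 carry the same note on phases (Table 2.09 lacks the comma): "Overall only, not split by study phase". Listing 22 has one programming note, a pointer to 11.5.3; no CRS flag is requested.

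On time spans, SAP 7 says: "Due to the long duration of the study safety summaries will be presented for the following time spans", and then names overall, dosing period, post dose to Week 6, and after Week 6. SAP 2.2 and Protocol 2 define the EBV reactivation endpoint over Day 21 to Month 24. Protocol 5.3.1 names fever as an objective and myalgia as a subjective CRS endpoint.

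**The concern.** CRS and EBV reactivation are the two safety risks named in the primary endpoint, and they mostly occur at different times. Protocol 3.3.2 places most infusion reactions in the earlier Phase II study in the first three treatment days. Protocol 3.4 puts the EBV viral load peak at about Week 3. A table that pools everything from first dose onward gives up that separation.

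Protocol 1.1 also expects more severe CRS at higher doses. If infusion fever rises with dose, Table 2.09 could show a dose-related rise in potentially EBV-associated symptoms even when later symptoms do not rise. Nothing in the table or in Listing 22 would mark which events the sponsor's own review had attributed to CRS.

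**Working it through.** The plan states no figure on this point, so there is none to reproduce. The check is mainly textual.

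**1. Do the two lists overlap?** The EBV list (SAP 11.5.3) has six terms. The CRS endpoints (Protocol 5.3.1) are fever, diarrhoea, vomiting, hypotension, headache, chills, nausea, arthralgia and myalgia. Pyrexia (fever) and myalgia are on both.

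**2. Does anything keep a dosing-period event out of Table 2.09?** Selection is by Preferred Term alone, so onset and CRS class play no part. A pyrexia or myalgia event on Days 1 to 6 that is classed as CRS enters both Table 2.08 and Table 2.09.

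**3. What do other displays recover?** Table 2.02 lists all AEs by Preferred Term, split by the SAP 11.3 phases, so pyrexia and myalgia can be read there by dose and phase. It gives neither the CRS class nor the number of patients with any of the six terms in each phase. Those need Listings 21 and 22 matched patient by patient.

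**4. Would a phase split alone isolate CRS?** No. Six daily doses run from Day 1 to Day 6. SAP 7 ends the dosing period on the last dose day (Day 6). SAP 11.3.1 ends it a day later: "Date of First Dose <= Date <= Date of Final Dose + 1" (Day 7). The CRS window runs for 14 days from first dose, so under 11.3.1 a CRS event on Days 8 to 14 falls in the phase from post-dose to Week 6. A flag is needed as well as the split, and Day 7 needs one rule.

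**5. How large could the effect be?** The documents give no symptom rate for these slow infusions, so every rate here is an assumption. Take 8 active patients per dose (SAP 2.3). Let c be the share with a listed symptom during dosing and e the share with one later, independent of each other.

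- Patients with any listed term overall: 8 × [1 − (1 − c)(1 − e)]
- Gain over later symptoms alone: 8 × c × (1 − e)

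At e = 0.10, later symptoms alone give 8 × 0.10 = 0.80.

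| c | Overall count | Gain |
|---|---|---|
| 0.10 | 8 × (1 − 0.810) = 1.52 | 0.72 |
| 0.25 | 8 × (1 − 0.675) = 2.60 | 1.80 |
| 0.50 | 8 × (1 − 0.450) = 4.40 | 3.60 |

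The gain shrinks as later symptoms become common. At c = 0.50 it is 8 × 0.50 × (1 − e) = 3.6, 3.0 and 2.0 at e = 0.10, 0.25 and 0.50. It covers all dosing-period listed symptoms. If only half of those patients had exclusively CRS-classed dosing-period events, the CRS part at e = 0.10 would be 0.36, 0.90 and 1.80.

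The formula presumes a count of patients with any of the six terms. The AE15 shell is not reproduced and no note requests that row, so whether Table 2.09 will print it is unknown.

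**The case against.** The strongest case for leaving the plan alone has several parts.

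- **The plan is a deliberate pair of views.** SAP 7.2 has CRS and EBV events appear both in the general AE tables, which are phase-split, and in separate focused outputs. Overall is one of the spans listed in SAP 7, and Table 2.08 is treated the same way. This stands: a reader might infer that Table 2.09 contradicts SAP 7, and it does not.
- **The trend is already visible.** Table 2.02 would show infusion fever rising with dose while later fever stays flat. This also stands. It would be too strong to say that a reader must match two listings to see it; only the CRS class and the per-patient total by phase are missing.
- **The inclusive list follows the protocol.** The six terms mirror Protocol Table 7, which has no onset window, and the title of Table 2.09 claims only a potential association. This is a good reason to remove no event, but not a reason to leave CRS-classed events unmarked.
- **Recording may avoid the overlap.** Protocol Appendix 4 has a diagnosis recorded in place of its symptoms, and a single CRS diagnosis would not enter Table 2.09. That is possible, but Protocol Table 5 grades symptom by symptom and the title of Table 2.08 refers to symptoms, so symptom-level records are to be expected.

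A reader might also infer a wider overlap from the verbatim examples in SAP 11.5.3: "High temperature, Feeling hot and cold & Shivering" under pyrexia and "Joint and muscle pain & Flu like symptoms" under myalgia, against the protocol's Grade 1 chills, "Mild sensation of cold; shivering; chattering of teeth". The documents do not support that step. The verbatim column does not select events, and an event coded to chills or arthralgia is not on the list.

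**Conclusion.** The gap is real but modest. As written, CRS-classed pyrexia and myalgia from the dosing period are counted, unmarked, in the only table dedicated to clinical EBV-type symptoms, and no other table supplies the per-patient separation.

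Its size is unknown. It depends on dosing-period symptom rates that the documents do not give, on symptoms being recorded individually, and on the antipyretic prophylaxis recommended for dosing days (Protocol 5.10.1.1), which may lower it.

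Two stronger inferences fail. The issue does not touch dosing: escalation rests on Protocol 5.3, and SAP 2.3 reports that a stopping criterion was already met in Cohort 3. Nor does it misclassify EBV reactivation: Protocol Table 8 does not count symptoms alone, and serology and viral load have their own displays (Tables 2.10 to 2.12 and Figure 2.02). What can still be improved is the clarity of the final report.

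**What to change.** Change the SAP only.

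1. Split Table 2.09 by the SAP 11.3 phases, as Table 2.02 already is. Keep the overall column and add a row for patients with any listed term.
2. In Listing 22, flag each event that the expert review classed as CRS. Also flag each imputed start date, because SAP 11.6.3 can move a partial date to Day 1 and so into the dosing phase.
3. Use one definition of the dosing period in SAP 7 and SAP 11.3.
4. Optionally, add a row for patients whose listed events are all CRS-classed.

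Do not remove events or impose a Day 21 cut-off. With viral load peaking around Week 3, earlier illness may be genuine.

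The cost is slightly more programming, on variables the SAP already defines. The CRS label comes from an unblinded sponsor team (Protocol 5.4), so the flag and any CRS-only row are added information and not a corrected count.
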